4.4 Maximum tolerated dose-determining population (Phase 1 dose escalation portion)

The MTD-determining population includes all patients from the safety set who meet the following minimum criteria during the first 28-day treatment cycle (Cycle 1):

- Received at least one dose of BAL101553 and has experienced a DLT.
- Received at least 24 of the scheduled 28 doses for q24h BAL101553 administration, or at least 48 of the scheduled 56 doses for q12h BAL101553 administration, without experiencing a DLT (including the ability to initiate treatment Cycle 2), have been observed for \geq 28 days following the first dose and have been evaluated for safety.

Patients who do not meet these minimum evaluation requirements will be regarded as ineligible for the MTD-determining population. These patients will be included in the full analysis/safety population but will be excluded from the calculation of DLT incidence and will be replaced by recruitment of additional patients.

Patients who received less than 85% of the scheduled doses (i.e., less than 24 of the scheduled 28 doses using a once-daily regimen, or less than 48 out of the scheduled 56 doses using a twice-daily regimen) during Cycle 1, will only be considered as valid for the MDT-determining population if these patients experience a subsequent DLT during Cycle 1. Patients who have received a lower than assigned dose and have tolerated BAL101553 without a DLT will be excluded from the MTD determining population, as the toxicity assessment is not considered to be representative for the originally assigned dose level.

Patients who receive more than 125% of the assigned dose during Cycle 1 (total dose for the 28-day cycle), e.g., due to an administration error, will only be considered as valid for the MTD determining population if these patients experience no subsequent DLT during Cycle 1.

4.5 Pharmacokinetic analysis population(PK)

The PK analysis set includes all patients who received at least one dose of study drug and had at least one post-baseline PK assessment.

4.6 Efficacy-evaluable population (Phase 2a expansion portion of the study, Simon's two-stage design)

The efficacy evaluable population (EEP) is the subset of the FAP who had at least one post baseline RANO assessment after having received at least 6 weeks of study treatment.

For objective response rate and stage transition, the analysis will be based on patients with measurable disease at baseline in the EEP.

5 STATISTICAL CONSIDERATIONS AND ANALYSIS

5.1 Derived variables

The following derived variables will be applied throughout the study:

- Baseline is defined as the last available assessment prior to first dose intake (including unscheduled assessments), e.g. Cycle 1 Day 1 pre-dose.
- Last/Final for safety is the first available value after treatment or, if not available, then immediately before last treatment.
- Adverse event (AE) duration (in days) will be calculated as (the times will not be considered): Event end date - Event onset date + 1.
- The following algorithm will be used for the study day determination:
 - Day 1 = Day of first study drug administration (i.e. at Cycle 1 Day 1). The day before day 1 is day-1.
 - Prior to Day 1 the algorithm is (<visit/examination date> minus <date of first study drug administration >)
 - Day 1 and subsequent days = (<visit/examination date> minus <date of first study drug administration >) + 1.
- Duration of exposure (in days) will be calculated as: Date of last study drug administration – Date of first study drug administration + 1.
- The response according to RECIST or RANO criteria will be as reported in the Case report form (CRF).

5.2 Handling of missing data and/or invalid data and outliers

5.2.1 Handling of missing response

Patients whose response (RECIST or RANO) is unknown or not reported will be treated as non-responders for summarizing the overall response rate.

5.2.2 Handling of missing or incomplete dates

Incomplete/partial dates will be replaced by derived variables and imputed using the following rules:

- if the day of the month is missing it is imputed to be the 15th if not in the month of treatment
- if both the day and month are missing, they are imputed to be June 30 if not in year of treatment
- missing years will be left as missing

In case this leads to inconsistencies with other available patient's data, the imputation values will be handled case-by-case.

6 STATISTICAL PLAN AND METHODS

Separate analyses will be provided for patients with advanced or recurrent solid tumors and for patients with recurrent or progressive GBM or high-grade glioma (phase 1 dose escalation), and for patients with recurrent GBM (phase 2a). Data will be listed by study phase and disease subgroup.

Data from all participating study centers will be combined for analysis. The core study report will include patient data until the time point when the last patient has completed at least two cycles of treatment or discontinued the study.

In the case that patients continue to receive study drug past this time (in accordance with the protocol) an extension report may be prepared once these patients have completed treatment, or have been discontinued.

The statistical analysis will be performed using the software package SAS version 9.4 or higher (SAS Institute Inc., Cary, NC 27513, USA). All individual data as well as results of statistical analyses will be presented in individual patient data listings and statistical summary tables.

In general, continuous variables will be summarized using the following standard descriptive summary statistics: mean, standard deviation, median, minimum, maximum and number of observations. Categorical data will be described using frequency and percentage. Shift tables will be provided, where appropriate. One additional decimal point for mean, median, Q1 and Q3 and 2 additional decimal points for SD will be used. Percentages will be rounded to one decimal place. Unscheduled assessments will only be listed and will not be included in the tables, unless otherwise specified. Any changes in the planned statistical methods will be documented in the clinical study report.

The following international dictionaries will be used for medical coding:

- Medical History events: MedDRA (version 19.1 or later version)
- Medications: WHO Drug Dictionary (March 1st, 2016 – Format B2 or later version)
- AEs: MedDRA (version 19.1 or later version)

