Patients who provide informed consent will undergo screening evaluations to determine eligibility. Informed consent must be obtained within the 28 days prior to the first administration of study drug. Screening assessments will be initiated and completed within the 15 days prior to the first dose of study drug (except for radiology assessments, see Section 5.6).

In the Phase 2a portion of the study patients with recurrent glioblastoma must have evaluable disease, defined by contrast-enhancing MRI, within 15 days prior to starting study drug.

BAL101553 capsules will be given to fasted patients once or twice daily (depending on observed pharmacokinetics and clinical safety), continuously, until disease progression, unacceptable toxicity, or another reason for withdrawal from study drug occurs (see Section 4.4). A treatment cycle will be defined as one 28-day treatment period; there will be no treatment-free interval between treatment cycles.

Administration

Oral as hard capsules.

Phase 1 dose escalation portion (enrollment completed)

The starting daily dose of BAL101553 in patients with advanced or recurrent solid tumors was 2 mg/day BAL101553 (corresponding to approximately 1 mg/m²), based on Good Laboratory Practice (GLP) toxicology studies. Dose cohorts comprised three patients per cohort, unless a drug-related DLT was observed in any patient, at which point the cohort was expanded [up] to six patients. For all cohorts, dose increments between cohorts, ranging from 30–100%, were based on the extent and severity of observed drug toxicity.

Patients with recurrent or progressive GBM or high-grade glioma are analyzed as part of a separate dose-escalation scheme. The starting dose for the first GBM/glioma cohort was 8 mg/day and was based on the observed clinical safety in completed solid-tumor patient dose cohorts.

Dose escalation was performed in fasted patients using an accelerated 3+3 titration design (see Table 3 and Section 3.1.2.1). Details of the dose escalation process are provided in Section 3.2.1 (including intrapatient dose escalation). DLT definitions are provided in Section 3.2.2. The starting dose rationale is described in Section 1.5.3.

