5.3.5 Overall survival follow-up

Survival follow-up in the Phase 2a portion will start the day of the last dose of study drug. All patients and/or family will be contacted at 3-month intervals (±14 days), with the patient status to be recorded as *Alive* (date); *Dead* (date); *Alive*, *but withdrew consent for further follow up* (last date under consent); or *Lost to Follow Up* (date of last contact). Survival updates may be made more often than every 3 months if the patient is seen at the investigational site for other reasons, and for overall study status assessments. The survival follow-up period will continue until the study has been completed (see Section 9.5), or other discontinuation criteria are met (see Section 4.4).

Note: Survival follow-up can be done either over the telephone, or by collection of public records in accordance with local laws.

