8.3.2 Statistical analyses

Data from all participating study centers will be combined for analysis. The core study report will include patient data until the time point when the last patient has completed at least two cycles of treatment or discontinued the study.

In the case that patients continue to receive study drug past this time (in accordance with the protocol) an extension report will be prepared once these patients have completed the study, or have been discontinued.

An interim analysis for stage transition in the Phase 2a dose expansion portion will be performed when the specified number of patients required for Stage 1 had at least one post-baseline RANO assessment after having received at least 6 weeks of study treatment, but no later than after the completion of Cycle 12.

If the required number of responses has not been observed at the time of enrollment of the last patient in Stage 1, enrollment may be suspended, or the cohort may be terminated due to apparent futility. If the required number of responses is reached earlier, the interim analysis may be performed earlier, and stage transition may occur based on a joint decision taken by the Investigators and the Sponsor (see Section 3.1.3).

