6.2.3 Progression-free survival

Progression-free survival is defined as the interval between the date of first infusion and the earliest date of objective disease progression according to RECIST criteria v1.1 for patients with advanced or recurrent solid tumors, and based on RANO criteria for patients with recurrent or progressive GBM/high-grade glioma; or Investigator-confirmed clinical progression; or death due to any cause in the absence of progression. Patients who have not progressed or died at EOS will be censored at the time of their latest objective tumor assessment.

If a patient has no post-baseline objective tumor assessment then the PFS will be censored to 0 day.

Progression-free survival will be summarized for the FAP (Phase 1 portion of the study) by disease subgroup and dose cohort.

In the Phase 2a portion of the study (Simon's two-stage design), PFS will be summarized for the FAP and EEP. Median PFS and PFS at 6 months after start of study drug treatment (PFS6) will be assessed in the Phase 2a portion of the study (Simon's two-stage design), using KM method. The 95% CI will be calculated with Brookmeyer-Crowley method. The associated survival curve will be displayed.

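### The core-report cut-off can fall 56 days after the last first dose, which weakens PFS6 and OS, and no update for patients off drug is specified

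*SAP*

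**What the plan says.** Protocol 8.3.2 and SAP section 6 use the same core-report rule: "The core study report will include patient data until the time point when the last patient has completed at least two cycles of treatment", with discontinuation as the alternative. The synopsis gives the cycle length: "A treatment cycle will be defined as one 28-day treatment period".

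Both documents provide for a later report only where patients are still receiving study drug after that point, and they differ on whether and when it is written:

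- Protocol 8.3.2: "an extension report will be prepared once these patients have completed the study, or have been discontinued".
- SAP section 6: "an extension report may be prepared once these patients have completed treatment, or have been discontinued".

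SAP section 7 nevertheless records changes from the protocol's planned analysis as not applicable.

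For the endpoints, SAP 6.2.3 states: "Median PFS and PFS at 6 months after start of study drug treatment (PFS6) will be assessed in the Phase 2a portion", by Kaplan-Meier, with patients who have neither progressed nor died censored at their latest objective tumor assessment. SAP 6.2.4 summarizes OS by Kaplan-Meier in the FAP and EEP and gives no data cut-off. Protocol 5.3.5 starts survival follow-up at the last dose: "All patients and/or family will be contacted at 3-month intervals (±14 days"). It runs until study completion, and Protocol 8.2 ends the study at the last study-related contact with any patient. SAP 3.4 says that Phase 2a is analyzed after data cleaning and lock, but does not date the lock.

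**The concern.** The cut-off is tied to the treatment needed for response assessment, but the same report carries endpoints that need longer observation. PFS, PFS6 and OS are the main secondary endpoints of Phase 2a. Up to 15 of the 34 planned patients have non-measurable disease and, according to the synopsis, contribute only to secondary endpoints, so much of what they add to efficacy depends on this follow-up.

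The extension report does not reliably close the gap. If nobody is on drug at the cut-off, it is not due. If it is due, neither document says that it will re-estimate PFS, PFS6 or OS, or that it will cover patients who have stopped drug and are in survival follow-up. Those patients and their families are contacted every 3 months, and no analysis is named for what is learned after the cut-off.

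**Working it through.** **The plan's own figures.** Neither document states a precision, event count or minimum follow-up for PFS6 or OS. The only operating characteristics given are those of the Simon design on response (SAP 3.3.3): type I error 3.7% at a 14% response rate and power 81% at 40%. The probability of rejection is the sum over x = 2 to 9 of C(9,x)·p^x·(1−p)^(9−x) · P(Bin(10,p) ≥ 6−x). It gives 0.0371 at p = 0.14 and 0.8132 at p = 0.40. Both figures reproduce, and the cut-off for time-to-event endpoints does not affect them.

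**Timing gap.**
- Earliest cut-off if the last patient completes two cycles: 2 × 28 = 56 days after the last first dose. If that patient discontinues sooner, the wording allows an earlier date.
- PFS6 horizon: 365.25/2 ≈ 183 days.
- Gap: 183 − 56 ≈ 127 days, or 127/30.44 ≈ 4.2 months.

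Patients who start in the last 4.2 months of accrual therefore cannot have 6 months of follow-up in a core report at the earliest cut-off. Phase 2a scans fall in the last two weeks of even-numbered cycles (SAP Table 3, note 12). The last entrants, if event-free, are thus censored at the Cycle 2 scan, at about weeks 6–8.

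**How many patients.** Accrual length is not given. Assuming uniform entry of 34 patients over A months, the number with under 6 months' potential follow-up is 34 × 4.16/A:

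| A (months) | Share | Patients of 34 |
|---|---|---|
| 12 | 35% | 12 |
| 18 | 23% | 8 |
| 24 | 17% | 6 |
| 36 | 12% | 4 |

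**How many of these are event-free.** Patients who progressed or died before the cut-off contribute fully. Assume exponential PFS with median m (not in the documents) and potential follow-up uniform between 1.84 and 6 months. The event-free share is then [exp(−1.84λ) − exp(−6λ)]/(4.16λ), with λ = ln 2/m. For m = 2 this is (0.529 − 0.125)/1.442 = 0.28. For m = 4 it is (0.727 − 0.354)/0.721 = 0.52. Applied to 11.8, 7.9, 5.9 and 3.9 patients, this gives about 3–6, 2–4, 2–3 and 1–2 patients.

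**OS at the same cut-off.** Assume exponential OS with a median of 6 to 10 months and the same accrual range. The share of deaths observed is 1 − [exp(−1.84λ) − exp(−(A+1.84)λ)]/(Aλ). It runs from 0.40 (median 10, A = 12) to 0.81 (median 6, A = 36), leaving about 20 to 7 of 34 patients alive.

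**Why a 6-month cut-off is not late enough.** The Cycle 6 scan falls at about day 154–168 and the next, at the end of Cycle 8, at about day 210–224. With a cut-off at day 183, the last event-free entrants would still be censored at the Cycle 6 scan, before the PFS6 time point.

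**The case against.** Several limits on this point stand.

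- A reader might infer that late entrants can never reach PFS6. That is true of the core report only. Treatment continues until progression or unacceptable toxicity, so late entrants who are progression-free will mostly still be on drug. They are the group whose continued treatment triggers the extension report, and the protocol commits to that report. With SAP section 7 declaring no change, the SAP's *may* can be read as a drafting slip.
- Two cycles is expressed as a minimum, so the actual cut-off may be later.
- Kaplan-Meier keeps PFS6 estimable from earlier entrants. The loss is one of precision.
- A reader might take the 12 to 4 patients as lost. They are patients with short potential follow-up, and many would already have had an event. Thirty-four is also a maximum. Short accrual looks optimistic as well: at the stated 2–4% EB1 prevalence (25–50 tissues per positive case), 34 positives need about 34 × 25 = 850 to 34 × 50 = 1,700 screened tissues.
- A reader might infer that later OS data are excluded from analysis. The undated lock in SAP 3.4 and the protocol's reference to study completion leave room for a later OS analysis. It is unspecified, not ruled out.
- A reader might infer that these estimates drive the decision to develop further. Protocol 1.5.2.2.1 names OS and PFS as primary endpoints of a potential later trial. The go/no-go criteria here come from the Simon design on response.

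What the objection does not remove is that the stated rule allows an early cut-off, that the later report's content is undefined and its status differs between the documents, and that patients off drug do not trigger it.

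**Conclusion.** The point holds as a cheap improvement to the secondary analyses. At the earliest permitted cut-off, Phase 2a patients from the last 4.2 months of accrual have under 6 months' potential follow-up: about 12 to 4 of 34 for uniform accrual over 12 to 36 months. Perhaps 6 to 1 of them would be event-free, if median PFS is 2–4 months. OS would be immature, with about 20 to 7 of 34 patients alive under medians of 6–10 months. Accrual pattern and medians are assumptions; the 56-day and 6-month figures come from the documents.

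The conflict between the protocol and the SAP over the extension report needs no assumption, and neither does the missing analysis of survival data collected after the cut-off in patients off drug. The response analysis, the stage decision and the Simon error rates are unaffected.

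**What to change.** 1. In SAP section 6, restore the protocol's *will* and its timing at study completion. State that the later report gives updated PFS, PFS6 and OS for the whole Phase 2a FAP and EEP, on or off drug, at the end of survival follow-up. If a departure from the protocol is intended, declare it in SAP section 7.
2. Set the Phase 2a data cut-off for PFS, PFS6 and OS no earlier than the last patient's first scheduled tumor assessment after 6 months from first dose, or progression, death or withdrawal if earlier. On the 8-week schedule this is about day 210–224. If scans move to 12-week intervals after Cycle 6, it is about day 238–252 (154 + 84 to 168 + 84).
3. State that response and stage-transition decisions keep their current timing, and relate the data lock in SAP 3.4 to these cut-offs.

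The cost is delay to the secondary time-to-event results. Against a day-56 cut-off it is 154–168 days (5.1–5.5 months) on 8-week scans, or 182–196 days (6.0–6.4 months) on 12-week scans, so about 5 to 6 months. No extra patients, scans or survival contacts are needed.

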6.1 Background characteristics

6.1.1 Patient disposition

Enrollment and disposition data will be presented for each patient in data listings and summarized by frequency tables for all enrolled patients.

Inclusion and exclusion criteria violations and patient enrollment eligibility will be listed.

6.1.2 Protocol deviations

All important protocol deviations reported by the clinical team will be presented in a data listing. Protocol deviations will be reviewed prior to database.

6.1.3 Demographic and baseline characteristics

Background and demographic characteristics of the FAP and EEP for phase 2a including age, sex, race, patient status at selection, female of child-bearing potential, reason not of childbearing potential, height, weight, body surface area (BSA), tumor type, previous anticancer treatments, medical conditions, performance status etc. will be summarized by dose cohort using descriptive statistics or frequency tables. Percentages will be based on the number of patients with available observations in the FAP and EEP for phase 2a.

Demographic information will be presented in data listings.

6.1.4 Medical history

Previous or current diseases as well as previous cancer treatments will be presented in data listings.

Medical history data will be summarized by dose cohort, system organ class (SOC) and preferred term (PT) using the FAP for and EEP for phase 2a.

6.2 Efficacy analysis

6.2.1 Objective response rate

The objective response rate will be calculated within the FAP (Phase 1 portion of the study), as the proportion of patients responding (i.e., with a best observed objective response of complete response (CR) or partial response (PR), based on RECIST criteria v1.1 for patients with advanced or recurrent solid tumors); and based on RANO criteria for patients with recurrent or progressive GBM/high-grade glioma.

In the Phase 2a portion of the study (Simon's two-stage design), the patients with measurable disease at baseline in the EEP will be the primary population for the calculation of the objective response rate.

A patient who has a response unknown or not reported will be treated as non-responder.

The proportion and its exact 95% confidence interval (CI) will be presented by disease subgroup and by dose cohort.

Waterfall plots, spider plots and swimmer plot summarizing tumor size, best response and treatment duration will also be provided.

6.2.2 Disease control rate

The disease control rate will be calculated within the FAP (Phase 1 portion of the study), as the proportion of patients with disease controlled (i.e., best response of CR, PR, or stable disease (SD)).

A patient who has a response unknown or not reported will be treated as non-responder.

The proportion and its exact 95% CI will be presented by disease subgroup and dose cohort.

In the Phase 2a portion of the study (Simon's two-stage design), the EEP will be the primary population for the calculation of the disease control rate.

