- 12. Women of child-bearing potential must have a negative serum pregnancy test (hCG) at Screening, and negative serum or urine pregnancy test (hCG) prior to BAL101553 dosing on D1 of every cycle. Screening labs performed ≤ 72 h prior to first dosing, and labs performed within the 24 h prior to all other in-clinic dosing days, do not need to be repeated (see Sections 5.5.7.6 and 7.3).
- 13. Tumor assessment by radiological exam (CT/MRI scans) will be performed at Screening, or within the 35 days prior to D1 for patients with advanced or recurrent solid tumors and within the 15 days prior to D1 for patients with recurrent or progressive GBM or high-grade glioma; and within the 7 days prior to completion of every even-numbered cycle, before administration of the next cycle of BAL101553. From Cycle 6 onwards, the interval between CT/MRI scans may be extended from 8 weeks to 12 weeks. End of Study assessment does not need to be repeated if an assessment was done within the 35 days prior.

BAL101553 Clinical Study Protocol CDI-CS-002

Version 11.0 1 July 2021, page 65 of 135

- 14. CA-125 or PSA in patients with non-measurable ovarian or prostate tumors will be assessed at Screening and must be repeated within the 7 days prior to completion of every cycle, before administration of the next cycle of BAL101553. End of Study assessment does not need to be repeated if an assessment was done within the 14 days prior.
- 15. Patients must fast ≥ 4 h prior to and ≥ 1 h after each BAL101553 administration.
- 16. AE (including SAE) monitoring must be continued for at least 28 days following the last dose of study treatment. SAEs need to be reported from the time of informed consent to allow for an assessment of serious procedure related events, i.e., serious events/complications related to the screening study procedures. Non-serious AEs will be collected from the time of first study drug administration. Non-serious AEs that occur between informed consent and first study drug administration will be collected as pre-dose medical history.
- 17. Blood PK samples will be collected from all patients as follows (see Section 5.7.1):

Dose escalation portion (Phase 1) of the study (see Sections 3.1.2):

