8.3.2.6 Disease control rate

The disease control rate will be calculated within the FAP (Phase 1 portion of the study), as the proportion of patients with disease controlled (i.e., complete response, partial response, or stable disease) after two treatment cycles, after four treatment cycles, and at the end of treatment. The proportion and its exact 95% confidence interval will be presented by dose cohort and by disease subgroup if appropriate.

In the Phase 2a portion of the study (Simon's two-stage design), the EEP will be the primary population for the calculation of the disease control rate.

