2 INTRODUCTION

This statistical analysis plan covers the detailed procedures for performing the statistical analyses and producing tables, listings and figures in the study described in Basilea Pharmaceutica International Ltd. (Basilea) Protocol CDI-CS-002, version 11.0 dated July 1st, 2021.

Considering that no patient was evaluated using Prostate specific antigen (PSA) or Cancer antigen-125 (CA-125), none of the analyses specified in the protocol based on these criteria will be detailed in this SAP.

The design and analysis of data for the surgical cohort mentioned in the protocol is also not included in this SAP, as a separate protocol amendment would be created when applicable.

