7 CHANGES FROM THE PLANNED ANALYSIS IN STUDY PROTOCOL

Not applicable.

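### Disease control rate: the protocol sets three time points, SAP 6.2.2 substitutes one best-response rate, and SAP Section 7 declares no change

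*SAP*

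**What the plan says.** Protocol 8.3.2.6 defines the disease control rate as the proportion of patients with complete response, partial response or stable disease "after two treatment cycles, after four treatment cycles, and at the end of treatment". That sentence concerns the Phase 1 full analysis population (FAP). For Phase 2a the section adds only that "the EEP will be the primary population for the calculation of the disease control rate". It gives no separate Phase 2a definition, so the time points carry over by implication.

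SAP 6.2.2 keeps the Phase 1 FAP, the exact 95% interval, the breakdown by disease subgroup and dose cohort, and the efficacy-evaluable population (EEP) for Phase 2a. The definition itself becomes "best response of CR, PR, or stable disease (SD". No time point appears there, and no other SAP section restores one. SAP 6.2.2 also treats an unknown or unreported response as a non-response.

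The SAP introduction says it implements "Protocol CDI-CS-002, version 11.0 dated July 1st, 2021", the same version as the protocol under review. SAP Section 7, on changes from the protocol's planned analysis, reads "Not applicable". SAP Section 6 adds: "Any changes in the planned statistical methods will be documented in the clinical study report".

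**The concern.** The two definitions answer different questions. The protocol's rates say how many patients are controlled at successive points. The SAP's rate says how many were ever controlled. A patient who is stable at the end of Cycle 2 and has progressed by the end of Cycle 4 counts as controlled under the SAP and has no later entry that shows the loss.

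The protocol's wording does not look accidental. The section just before it, 8.3.2.5, defines objective response by best observed response, and 8.3.2.6 then uses time points for disease control. The SAP merges the two ideas.

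At stake is whether the reported rate is the one that was planned. A reader who relies on Section 7 would take the SAP figure to be the protocol's rate. The SAP introduction does disclose another departure, the dropping of PSA and CA-125 analyses, so silence on this one reads as confirmation that nothing changed.

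**Working it through.** **1. The texts side by side**

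| Item | Protocol 8.3.2.6 | SAP 6.2.2 |
|---|---|---|
| Controlled means | CR, PR or SD | CR, PR or SD |
| When | After 2 cycles, after 4 cycles, end of treatment | Best response, no time point |
| Rates reported | Three | One |
| Phase 1 population | FAP | FAP |
| Phase 2a population | EEP | EEP |
| Declared in SAP Section 7 | n/a | No |

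Only the timing differs, and it is not declared.

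**2. Direction.** Use the same denominator for both rates. Any patient with CR, PR or SD after two cycles has a best response of at least SD. The patients controlled after two cycles are therefore a subset of those controlled by best response, and the best-response rate is at least the two-cycle rate.

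It will often lie close to that rate. In Phase 1 the scheduled scans fall "within the 7 days prior to completion of every even-numbered cycle, before administration of the next cycle of BAL101553" (Protocol Table 8, footnote 13), and in Phase 2a within the last two weeks of even-numbered cycles (Table 9, footnote 12). The first scheduled scan is thus the protocol's own first time point.

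The best-response rate can also be higher. A patient may stop during Cycle 2, before the scheduled scan, and show stable disease on the End of Study scan, which Protocol 5.3.3 requires if there was none in the previous 35 days. That patient is controlled under the SAP but has no two-cycle assessment.

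**3. The plan's own figures.** Neither document states a figure for disease control, so there is none to reproduce. The only design figures belong to objective response: type I error 3.7% and power 81%. The exact sum over x = 2 to 9 of P(X1 = x) × P(X2 ≥ 6 − x), with 9 and then 10 patients, gives 0.0371 at a 14% response rate and 0.8132 at 40%. Both reproduce. Neither uses the disease control rate.

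**4. Illustration of size.** Assumptions, none from the documents: exponential PFS, median m of 3 or 4 months (91.3 or 121.75 days at 30.44 days per month), every patient assessed, scans at 56 and 112 days. Then S(t) = 2^(−t/m).

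- m = 3 months: S(56) = 2^(−56/91.3) = 0.65; S(112) = 0.65371² = 0.43.
- m = 4 months: S(56) = 2^(−56/121.75) = 0.73; S(112) = 0.72701² = 0.53.

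Under this model S(112) = S(56)², so the gap between the two-cycle and four-cycle rates is s(1 − s) with s = S(56). That is about 23 points at 3 months (0.654 − 0.427) and 20 points at 4 months (0.727 − 0.529). It cannot exceed 25 points. Medians of 6 to 16 weeks give gaps of about 21 to 25 points. With a median of 8 weeks and the 28 GBM or high-grade glioma patients dosed in Phase 1, the expected counts are 14/28 (exact 95% interval 31-69%) after two cycles and 7/28 (11-45%) after four. The single SAP rate would sit near the first figure.

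**The case against.** The best reply is that little depends on this rate. Disease control is not listed as an endpoint in Protocol 8.1 or SAP 3.2, and the Simon stop/go rule uses objective response only. The time points sit in the Phase 1 sentence, and the protocol synopsis presents disease control without any. Phase 1 dose cohorts had 3 to 8 patients (Protocol Table 22), so by-cohort intervals are very wide under either definition. All of this stands and limits the weight of the point.

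A reader might go further and infer that the SAP conceals how long control lasts. The documents do not support that. SAP 6.2.3 summarizes PFS for Phase 1, where Protocol 8.3.2.7 only lists it, and gives Kaplan-Meier median PFS, PFS at 6 months and a curve for Phase 2a. SAP 6.2.1 adds spider and swimmer plots, and SAP Section 6 provides individual listings. Time information leaves the disease control rate, not the report. Nor do the documents show any motive for the change.

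Two further objections hold in part. The end-of-treatment rate says little about durability, because treatment generally continues until progression; it is nevertheless one of the rates the protocol specified. And the illustration does not describe the Phase 2a EEP, which requires a RANO assessment after at least 6 weeks of treatment.

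The promise in SAP Section 6 to document changes in the study report does not answer the point. Section 7 is a statement about the SAP as it stands, and it is wrong.

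**Conclusion.** The discrepancy is certain from the text. SAP 6.2.2 replaces three protocol rates with one best-response rate, and SAP Section 7 declares no change. The conflict is explicit for the Phase 1 FAP and implied for the Phase 2a EEP. The direction is also certain on a common denominator: the SAP rate is never below the two-cycle rate.

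The size is not known, because the documents give no disease control data and no expected PFS. The 65-73% at 8 weeks and 43-53% at 16 weeks rest wholly on an assumed exponential PFS with a median of 3 to 4 months and complete assessment. They show what a single rate can leave out and do not predict this trial's results. No error rate, stopping decision or listed endpoint is affected. This is a consistency fault in a secondary summary, worth correcting because the correction is cheap.

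**What to change.** In SAP 6.2.2, compute the disease control rate after two cycles, after four cycles and at end of treatment, each with its exact 95% interval, and say whether the time points also apply to the Phase 2a EEP. Count patients who are off treatment or unassessed at a time point as not controlled, in line with the SAP's rule for unknown response. At end of treatment only the unassessed part of that rule applies. Also state how patients are handled who have not yet reached a time point at the data cut-off, since the core report may close when the last patient has completed two cycles.

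Keep the best-response rate only as an added row, and replace the entry in SAP Section 7 with a declaration of that addition.

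The cost is a few lines of SAP text and two or three table rows. Scans already fall at the end of Cycles 2 and 4 and at the End of Study visit, so no new data are needed. The later rates will look less favourable, and the rule for patients off treatment is conservative for those who stop without progression; a footnote with their number would make that visible.
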